### Subject: Expedited Review

Thank you for allowing me to review an addendum proposal entitled "Availability of A2 from Mola Fish in human serum after Mola Fish meal" to the Protocol # 2001-025 titled "The efficacy of Vitamin A- rich small fish in improving vitamin A status in children in Bangladesh" by Mr. [name].

Objective: To demonstrate the presence of A2 in the serum after eating Mola Fish.

I have reviewed the proposal. The PI has given a strong-justification to measure Vitamin -A2 in serum after eating Molla Fish in this addendum proposal. However, I have the following comments:

1. In "Methods and materials" the PI has stated that the volunteers will be discouraged to eat any other fish particularly small fish like Mola during the 6-weeks study period. They will also be requested to refrain from taking any vitamin Pills which may contain Vitamin A. However, the PI has not mentioned anything about intake of foods of animal origin which contain preformed Vitamin A and is more efficiently absorbed.
2. The PI has enclosed the English version of consent form and mentioned in his memo to ERC Chair that since the 5 study participants (including the PI) are the employers of ICDDR,B the consent form is not required to be in Bangla but will be in English only. There is no objection in principle to have consent form in English provided the study participants can comprehend English well.

Not  
relevant.

only those  
volunteers have proficiency  
in English would be  
selected. [name]

The PI has not specified who are the potential 5 volunteers (except the PI) and their educational level. Without knowing the educational level it is difficult to have an idea

about their comprehension of consent form in English. The PI is required to provide information in this regard.

There is no other ethical concern with regard to this addendum proposal. Subject to clarifying the above two points, the proposal is recommended for approval.

Thank you again

① The reviewer might have confused with Retinol Vitamin (which is A1) with that of A2 which is only available (to our best knowledge) from fish (small fish and mola is one of them.)  
[name]

International Centre for Diarrhoeal Disease Research, Bangladesh  
CENTRE FOR HEALTH AND POPULATION RESEARCH  
Mail : ICDDR,B, [name]  
[contact], Telex : [name] ICDD BJ  
[contact], [name], [name], [name], [name], [name], [name]  
Cable : Cholera Dhaka

### Background

Mola fish has a high content of vitamin A (>2500 RE/100gm edible portion). Out of whole vitamin A in mola fish, about 20% is A1 and 70-80% A2 (didehydroretinol). A2 is a viscous alcohol that has less bioactivity (maximum 40% i.e. it competes with RBP) as compared to A1. Function wise, both A1 and A2 are almost same with the exception of the role of A1 on the retina. In our study (Protocol no. 2001-25), we fed sufficient mola fish to children who are marginally vitamin a deficient and expected an improvement of their vitamin A status (increase in serum retinol). The study is completed .It looks like that improvement in vitamin A status measured as serum retinol (A1) was not as expected.

	Serum Retinol umol/L		
	Mola Fish Gr	Rui with added Vit A(+Control)	Rui (-ve Control)
Pre	0.59±0.11	0.59±0.10	0.60±0.11
Post	0.60±0.18	0.84±0.20	0.65±0.25
	NS	<0.001	NS

**Note:** Preliminary data are being corrected for Acute Phase Protein.

However, none of the children in the mola fish group appeared to be clinically vitamin A deficient neither during study period nor at the end. Then the question comes to our mind that whether there was any absorption of A2 which is the major proportion of vitamin A in mola fish and that could have been demonstrated in the human blood. To our knowledge, there is no report documenting the presence of A2 from fish/food in the human blood although synthetic A2 could be measured after an oral dose. Measurement of A2 in the serum was not part of our original protocol. Normally A2 is also not found in the human blood.

**Objective:** To demonstrate the presence of A2 in the serum after eating mola fish.

### **Methods and materials:**

Five adult volunteers (ICDDR,B employees) including the investigator will eat lunch with mola fish for 6 days per week for 6 weeks. Volunteers will be discouraged to eat any other fish, particularly small fish like mola during the 6 weeks' period. It should be noted that most of the big fishes do not have A2. Also they will be requested to refrain from taking any vitamin pills which may contain vitamin A. We shall also collect information about any illnesses and medication during the 6 weeks period.

At the beginning and after the end of feeding, 1 ml venous blood will be collected. Serum will be separated and both A1 and A2 will be measured by HPLC following standard technique. The Nutritional Biochemistry Laboratory is equipped with the instrumentations and similar assay has been conducted before in the laboratory.

Mola fish after being usually cooked was found to have 770ug of All-trans 3,4 Didehydroretinol (A2) per 50 gm curry. We shall offer 150 gm mola curry correspond to 2300 ug A2 to each volunteer. Rice, Dal and Vegetable will be served will be *ad libitum*. Any left over of mola fish curry will be recorded. Each volunteer will act as his/her own control.

Informed consent (form enclosed) will be obtained.

**Rationale:** Since A1 and A2 are similar at least function wise , if we can demonstrate that substantial A2 is found in blood after mola fish meal, we can still advocate for consumption of mola fish and other vitamin A rich small fish to improve vitamin A irrespective of the fact that A1 in blood after consumption of Mola fish is not increased.

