Preformed vitamin A, which is found in foods of animal origin, is more efficiently absorbed than most carotenoids and more effective in improving vitamin A status (National Research Council, 1989). However, these foods are considered as not being easily available to and affordable for poor households. Within food based strategies, there has been no focus on the role that small fish can play in preventing and combating micronutrient deficiencies. Small fish is a commonly consumed food in many developing countries and are easily available, relatively cheap and well liked by most household members, including children. In Bangladesh, small fish rank third with respect to amount of raw food intake after rice and vegetables in many communities for large parts of the year ([name] *et al*, 1997). Some commonly consumed small fish species have been found to have extremely high contents of preformed vitamin A (Roos, 2001). For example, mola contains 2,400 - 3,000 RE/100 g raw edible fish (Roos, 2001), 5 times higher than the green leafy vegetable, amaranth (*Amaranthus gengeticuss*) (Varming, 1996). Few other indigenous small fish species in Bangladesh have been identified to have very high contents of vitamin A, chanda (*Parambassis baculis*) (> 1500 RE/100 g raw edible fish); dhela (*Osteobrama cotio cotio*) and darkina (*Esomus danricus*) (500-1,500 RE/100 g raw edible fish) while several other species have been found to have medium contents of vitamin A (100-500 RE/100 g raw edible fish) (Roos, 2001). However, the bioavailability of vitamin A from these small fish still needs to be established. An intake of 45 g mola/d (2,400 RE/100 g raw edible fish) meets the full daily vitamin A recommended dietary allowance of 4-6 years old children (500 RE/d) (National Research Council, 1989), taking a cooking loss of about 50 % into consideration. A pilot trial has shown that children can easily consume 45 g of fish (given as 60 g of fish curry) and even higher amounts, 70 g of fish (given as 90 g of fish curry) from a single main meal (own observations). No study has looked at the efficacy of a daily amount of vitamin A rich small fish on the vitamin A status in humans.

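### The A2 addendum can show that A2 from mola is absorbed in adults, but its Rationale treats that as grounds for advocating mola to improve vitamin A status; pre-feeding fish intake is also uncontrolled.

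*Protocol*

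**What the plan says.** The addendum's Background gives one objective: to show that A2 appears in serum after mola has been eaten. Its Methods and materials set out the design:

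- "Five adult volunteers (ICDDR,B employees) including the investigator will eat lunch with mola fish for 6 days per week for 6 weeks".
- "At the beginning and after the end of feeding, 1 ml venous blood will be collected", with A1 and A2 both assayed by HPLC.
- "Each volunteer will act as his/her own control".
- "Volunteers will be discouraged to eat any other fish, particularly small fish like mola during the 6 weeks' period". Nothing is said about fish eaten before the first sample.
- "Mola fish after being usually cooked was found to have 770ug of All-trans 3,4 Didehydroretinol (A2) per 50 gm curry", and 150 g of curry is offered per meal.

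The Rationale starts from the premise that A1 and A2 have similar functions. If substantial A2 is found in blood, it says, "we can still advocate for consumption of mola fish and other vitamin A rich small fish to improve vitamin A irrespective of the fact"; what it sets aside is the absence of any increase in serum A1. No threshold for substantial is given.

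The addendum's Background also states that "A2 is a viscous alcohol that has less bioactivity (maximum 40% i.e. it competes with RBP) as compared to A1". It exempts the retina from the functional similarity, says A2 is not normally found in human blood, and tabulates preliminary serum retinol from the completed children's trial.

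**The concern.** The objective is about absorption; the Rationale is about status. The step between them rests on evidence the addendum does not collect. The main trial concerns marginally vitamin A deficient children aged 3 to 7, with serum retinol as its primary basis. The addendum studies adult staff who are not selected for deficiency. A1 is assayed in the same samples, but the Rationale sets it aside in advance, so no vitamin A status measure enters the conclusion.

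At stake is what may be said publicly about mola. An absorption result could be presented as support for a status claim that the preliminary trial data do not provide.

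The second issue is attribution. With no concurrent control, the pre-feeding sample carries the whole comparison. A volunteer who ate small fish shortly before it may already have A2 in serum. The main Protocol's Background ranks small fish third in raw food intake in many communities for much of the year. The investigator's reply in the expedited-review memo says A2 is, to the team's best knowledge, available only from fish.

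**Working it through.** **1. The addendum's own figure.** A2 per adult meal = 770 µg / 50 g × 150 g = 2310 µg. The addendum states 2300 µg, so the figure reproduces to within 0.4%. No sample size calculation is given for the five volunteers, so there is none to check.

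**2. What five volunteers can establish.** In the best case, A2 is detected in 5 of 5. The exact two-sided 95% lower limit for the proportion of people with detectable A2 is 0.025^(1/5) = 0.478, or 47.8%. That is enough to show that absorption occurs. It says nothing about vitamin A status.

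**3. The status data the addendum quotes.** Mean serum retinol in µmol/L, preliminary and still being corrected for acute phase protein:

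- Mola: 0.60 − 0.59 = +0.01
- Rui with added vitamin A (positive control): 0.84 − 0.59 = +0.25
- Rui (negative control): 0.65 − 0.60 = +0.05
- Mola minus negative control: 0.01 − 0.05 = −0.04

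The positive control responded; mola showed no gain over the negative control.

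**4. The premise of similar function.** The same Background limits A2 bioactivity to at most 40% of A1 and excepts the retina. Eye damage and blindness are part of the main Protocol's stated motive. The premise is therefore qualified by the addendum's own text.

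**5. Intake compared with the children.** The children's curry portion is 90 g under Test meals. The main Background reports from the pilot that "children can easily consume 45 g of fish (given as 60 g of fish curry) and even higher amounts". These two portions need to be reconciled; no view is taken here on which is right.

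- Per meal: 150/90 = 1.67, or 150/60 = 2.50.
- Whole feeding period: adults 150 g × 36 meals = 5400 g; children 90 g × 54 = 4860 g, or 60 g × 54 = 3240 g. The ratios are 1.11 and 1.67.
- Per kg of body weight: no weights are given. Assuming adults of 45 to 70 kg and children of 12 to 18 kg, the per-meal ratio is about 0.3 to 1.0.

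The direction depends on the scale chosen. The supportable statement is that intake and population differ, so the adult result does not transfer directly.

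**6. Effect of earlier fish intake.** Let b be A2 in the first sample and e be A2 in the second. If b > 0 because of earlier fish, the change e − b understates the response to the study meals, and e alone cannot be attributed to them. Because b is measured, carry-over would be visible. It blurs attribution or shrinks the rise; it does not create a spurious one.

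**The case against.** The strongest reply is that the Rationale sentence is motivation, not an endpoint or analysis rule. It requires substantial A2, not merely any A2, and openly concedes that A1 did not rise. The work is a USD 2,704 exploratory add-on that changes no estimate in the completed trial. All of that stands and limits the weight of the point. It does not rescue the inference: substantial is undefined, and even a large serum A2 would be evidence of absorption.

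On fish intake, the baseline sample is assayed for A2, the addendum says A2 is not normally found in human blood, and the ranking of small fish describes communities, not these employees. That also stands, which is why this part is secondary.

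A reader might infer several stronger things that the documents do not support:

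- That the missing restriction threatens a false negative. The objective is presence of A2, and earlier intake would not hide presence.
- That a positive result would overturn the randomised comparison. The Rationale acknowledges the lack of an A1 rise, and the trial data are preliminary.
- That the adults are simply given more than the children. This is true per meal in grams, less so over the feeding period, and probably not per kg.
- That stored serum from the children could settle the matter. No document says any remains.

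**Conclusion.** The design is adequate for its stated objective. The Rationale is not supported: two serum samples from each of five adult staff, at a different intake and in a different population, can show that A2 from mola is absorbed. They cannot show that mola improves vitamin A status in marginally deficient children. The addendum's own limits on A2 activity, and its preliminary retinol difference of −0.04 µmol/L against the negative control, make the gap plain. This does not show that A2 is without value; it shows that the addendum does not test the matter.

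The late start of the fish restriction is a real but smaller weakness in attribution. Its size cannot be given, because the documents report neither the volunteers' fish intake nor how long A2 persists in serum. The retinol comparison rests on uncorrected preliminary means, and the per-kg range on assumed weights.

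**What to change.** 1. In the Rationale, remove the sentence that permits advocacy to improve vitamin A. State instead that serum A2 after the study meals would show that A2 from mola is absorbed in adults, and does not by itself show that mola improves vitamin A status in children.
2. Start the no-small-fish instruction before the first blood sample. The investigators should justify its length, as the documents give no clearance data.
3. State that the result will be judged on the change from the measured baseline A2 in each volunteer.

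The first and third changes are wording only. The second means an earlier instruction to five staff and a short delay. The price is a weaker permitted claim; the objective, feeding plan and assays stay as they are.

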**Budget: (USD)**

Personnel	1 FRA GS III	820.00
Cook		300.00
Lab cost (A1 and A2 analyses)		484.00
Food cost (Molafish+Rice+Misc)		400.00
Laboratory Supplies		150.00
Stationeries		150.00
Interdepartmental		200.00
Unforeseen		200.00
Total		<hr/> 2,704.00

International Centre for Diarrhoeal Disease Research, Bangladesh  
CENTRE FOR HEALTH AND POPULATION RESEARCH  
Mail : ICDDR, B, [name]  
[contact], Telex : [name] ICDD BJ  
[contact], [name], [name], [name], [name], [name], [name]  
Cable : Cholera Dhaka

## *Memorandum*

3 December 2001

To : Mr. [name]  
Laboratory Sciences Division

From: [name]  
Chairman, Ethical Review Committee (ERC)

A handwritten signature in cursive script, appearing to read '[name]', written in dark ink.

Sub: **Approval of protocol # 2001-025**

This is in reference to your memo of 3 December 2001 with the modified copy of your protocol # 2001-025 entitled "The efficacy of Vitamin A rich small fish in improving Vitamin A status in children in Bangladesh". The modified version of the protocol is hereby approved upon your satisfactory addressing of the issues raised by the ERC considered in its meeting held on 28th November 2001.

I wish you all the success in running the above mentioned study.

Copy: Acting Head  
Laboratory Sciences Division

International Centre for Diarrhoeal Disease Research, Bangladesh  
CENTRE FOR HEALTH AND POPULATION RESEARCH  
Mail : ICDDR, B, [name]  
[contact], Telex : [name] ICDD BJ  
[contact], [name], [name], [name], [name], [name], [name]  
Cable : Cholera Dhaka

Dec 03, 2001

To : Chairman, ERC  
From : [name] *[name]*  
Subject : Replies to queries raised by the ERC member regarding Protocol#2001-025

Thank you very much for your careful review and comments. Below are our replies:

1. Your advice to change the title is reasonable. However, please bear with us that if we change the title now, it should have to go to both RRC and the donor for their approval. Since the present title is implied, we would request your consideration to keep the title as it is.
2. The basis of the proposed efficacy trial for 9 weeks was the study carried out by de Pee et al (1998a).
3. You are right that VAC program is on for children upto 59 months. Our proposed age group is 3-7 years. We have observed out of a sample survey that the coverage is not that much. In any case, we shall not include any children have had vitamin A supplementation during last 6 months. We have already mentioned it clearly ( Pls see the consent form for feeding trial #3) that under those conditions we shall take out the children from the study and supplement them with Vitamin A.
4. At the end of the study all children will be supplemented with vitamin A. It is mentioned in both the text as well as in the consent form (Feeding Trial #4).
5. Yes, you are right. Our primary aim is the improvement in retinol status and accordingly sample size was calculated. For the other variables, data analysis plan has been described in page 21 of the protocol. Also handling of confounding factors are discussed in page 16.
6. We made it descriptive so that most questions are clear to the consent giver.
7. Please find now the Bangla version of the consent form.
8. It was an inadvertent mistakes. The serial number 10 and 11 would be 8 and 9. A corrected version is enclosed.
9. Thank you very much for pointing out the typo-error and few mistakes. The spelling errors are now corrected. Fresh abstract summary and consent form are also enclosed.

We hope, the protocol may please be approved now.

*I have gone through the responses by the investigators. The issues have been addressed and the protocol may be approved.*

*[name]*  
*03/12/2001*

## ABSTRACT SUMMARY FOR ETHICAL RESEARCH COMMITTEE (ERC)

Vitamin A deficiency (VAD) is a public health problem in many developing countries, including Bangladesh. Within food based strategies there has been no focus on the role of small fish in combating vitamin A and micronutrient deficiencies. Few commonly consumed small fish species have been found to have very high contents of preformed vitamin A. For example, mola (*Amblypharyngodon mola*) contains 2,400-3,000 RE/ 100-g raw edible fish. The *overall aim* of the study is to determine the change in vitamin A status after supplementation of 45 g of vitamin A rich small fish, mola (500 RE) in a daily meal for 9 weeks, to marginally vitamin A deficient Bangladeshi children (3-7 y) in a Dhaka slum, and compare it with the change in vitamin A status obtained after supplementation of 45 g of big fish, rui (*Labeo rohita*) containing no/little vitamin A and 45 g of big fish, rui with added retinyl palmitate (500 RE). Children (180) will be randomly allocated to either of three diet groups. Studies on the efficacy of commonly consumed vitamin A rich small fish on the vitamin A status in children are therefore valuable as a first step towards developing specific agricultural and food based programs. If this study is successful, there is a large scope to increase the production of mola and other small indigenous vitamin A rich fish in combating VAD. The finding of this study will be equally important for other developing countries with habitual fish consumption.

### 1. Requirments for the study group and rationale fir using this study group?

The subject population, children 3-7 y usually have marginal vitamin A deficiency and they are at great risk for such deficiency which may lead to nightblindness or complete blindness if they are not identified and effectively treated. Food based strategies are the best and sustainable. However, fish based food intervention was never tried. We are proposing here to intervene with small fish content of vitamin A to improve the vitamin A status. This age group of children can eat such small.

### 2. Describe and assess any potential risk?

There are no more than minimal risk involved in conducting the study.

Four ml blood sample will be collected and stool sample will be collected from study subjects at *screening*. A second blood sample (4 ml) will be collected at *endpoint* in subjects enrolled in the feeding trial. In a sub-sample, one fourth of the children enrolled in the feeding trial, two blood samples will be taken with an interval of 5 h at *baseline* and at *endpoint* for the Relative Dose Response test. Complications of blood drawing are generally minor but may have mild momentary discomfort.

Children enrolled in the negative control group (no/low vitamin A) will replace only one habitual meal per day by a no/ low vitamin A rich meal, while all other meals will be consumed at home, as normally done. The duration of the study is relatively short, 9 weeks, 6 days per week and no severely vitamin A deficient children (serum retinol concentration  $<0.35 \mu\text{mol/L}$ ) will be recruited. At the end of the study, the children will receive an oral dose of vitamin A supplementation.

Subjects will not be hospitalized and no other invasive technique will be applied that may cause physical, psychological, social or legal risks.

### 3. Procedures for protecting against or minimizing potential risks?

Disposable syringes and needles will be used for collecting blood for protecting or minimizing any risk. Well experienced personnel will perform blood drawing. Disposable plates will be used daily for serving the test meal

### 4. Method for safeguarding confidentiality or protecting anonymity?

All information collected will be kept strictly confidential. A unique number will be used for data presentation instead of child's name. Other than the investigators, no one will have access to any information of the children. The parents may however, will know the laboratory results, medical conditions and treatment if any.

5.

